9 STATISTICAL CONSIDERATIONS

9.1 General Design Issues

This will be prospective single arm pilot study. We propose enrolling 40 patients in this study.

Measure of success is post-treatment assessment with nasal swab sent for gram stain, culture and sensitivity.

9.2 Sample Size and Randomization

We propose enrolling 40 patients in this study. Since this study is a pilot study where we aim to describe the results and collect data for future larger study, sample size calculation is not required.

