Topical Antibiotics in Chronic Rhinosinusitis

NCT03673956

August 26, 2018

Topical Antibiotics in Chronic Rhinosinusitis

v3 8-26-18

i

PRÉCIS

Study Title

Topical Antibiotics in Chronic Rhinosinusitis

Objective

The primary objective is to show that the use of topical antibiotics in the treatment of chronic rhinosinusitis does not lead to antibiotic resistant organisms. The secondary objectives are to investigate the effects of topical antibiotics on patient symptoms as measured by the validated Sino-Nasal Outcomes Test (SNOT-22) and physical exam endoscopic findings as documented by Lund-Kennedy endoscopic scoring system.

Design and Outcomes

This is a prospective pilot study to evaluate development of antibiotic resistance in patients with chronic rhinosinusitis who are being treated with topical antibiotics.

Interventions and Duration

Intervention includes 28 days of culture directed antibiotic therapy with one of the following four topical antibiotics: Tobramycin, Mupirocin, Gentamicin or Levofloxacin

Sample Size and Population

There will be 20 participants total in the study and they will all receive the intervention.

STUDY TEAM ROSTER

Principal Investigator: [name]

[name], MD

[contact] [contact]

Co-Investigators:

[name] [contact]

[name] [contact]

Study Team:

[name] [contact]

[name], MS Biostatistician Phone:

[name], CCRP Research Coordinator

[name] Research Coordinator

Phone: Pager:

1 STUDY OBJECTIVES

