3 STUDY DESIGN

This is a prospective, pilot study to investigate the presence or absence of antibiotic resistant organisms after treatment of chronic rhinosinusitis with topical antibiotics. In addition, therapeutic effects of the topical antibiotics will be investigated via assessment of patient symptoms, and physical exam endoscopic findings.

There will be 1 study group with 20 patients.

The patients will first undergo pre-intervention assessment in the outpatient setting. This will occur in the Department of Otorhinolaryngology on the 12th floor of the Gonda building in Rochester, MN with one of the staff rhinologists. Patients will be selected to participate if they have active mucopurulence on their endoscopic examination. The assessment will consist of 1) obtaining a nasal swab of mucopurulence from the affected sinus to be sent for gram stain, culture and sensitivity, 2) assessment of patient symptom severity score as measured by the self-administered Sino-Nasal Outcomes Test (SNOT-22) survey, and 3) assessment of patient physical exam as evaluated by rigid nasal endoscopy and documented in Lund-Kennedy endoscopic findings form.

The study intervention is the administration of culture directed topical antibiotics over 28 days. These antibiotics will prescribed to the patient in capsule form as compounded by the Mayo Clinic pharmacy, or suitable licensed compounding pharmacy. One capsule will subsequently be added to a nasal saline irrigation bottle, and the patient will administer this irrigation to him or herself in the usual fashion twice per day.

- The dosages of the antibiotic capsules were determined by the Mayo Clinic pharmacy team with input from infectious disease, based upon available published data, and will be as follows, dissolved in a standard 240mL saline irrigation rinse
 - Mupirocin: 30 mg
 - Tobramycin: 192 mg
 - Gentamicin: 192 mg
 - Levofloxacin: 250mg

After the completion of the study intervention (within 21 days), the patient will undergo post-intervention assessment in the outpatient setting, again in the Department of Otorhinolaryngology with one of the staff rhinologists. The patient will again be assessed with 1) nasal swab from the affected sinus sent for gram stain, culture and sensitivity 2) SNOT-22 symptom scores and 3) Lund-Kennedy endoscopic exam scores.

SELECTION AND ENROLLMENT OF PARTICIPANTS 4

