6.2.2 Enrollment and Baseline

Enrollment

Enrollment will be defined as the date all screening criteria are met and individual agrees to participate. There will be a single informed consent form for both screening and study procedures. Enrollment and screening will be conducted during the same visit.

The criteria used for inclusion and exclusion will be collected from the patient on this date using the following tests:

- medication reconciliation
- Review of medical record

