8 INTERVENTION DISCONTINUATION

Participants may withdraw voluntarily from participation in the study at any time and for any reason. Participants should continue to be followed, with their permission, after study intervention has been administered.

Replacement of participants who discontinue early is allowed. The participants who are replaced will not be counted in the study and replacement can occur if participants do not complete the at least 48 / 56 dosages of intervention with topical antibiotics.

It is vital to collect safety data on any subject discontinued due to an AE or SAE. In any case, every effort will be made to undertake protocol-specified safety follow-up procedures. If voluntary withdrawal occurs, the subject will be asked to continue scheduled evaluations, complete an end-of-study evaluation, and be given appropriate care under medical supervision until the symptoms of any AE resolve or the subject's condition becomes stable.

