10.3.3 Protocol Deviations

Protocol deviations will be captured by the PI or study staff at the time of occurrence, during surgery or during follow up. Information on deviation will be documented. The study will only use data that is coherent with protocol.

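### The protocol sets the sample size at 20 in the précis and section 3 but at 40 in sections 9.1 and 9.2, and nothing reconciles the two

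*Combined protocol and SAP*

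**What the plan says.** All of the following is current text.

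- **Précis, Sample Size and Population:** "There will be 20 participants total in the study and they will all receive the intervention".
- **Section 3:** "There will be 1 study group with 20 patients".
- **Section 9.1:** "This will be prospective single arm pilot study. We propose enrolling 40 patients in this study".
- **Section 9.2:** "We propose enrolling 40 patients in this study". It adds that a sample size calculation is unnecessary because the study is a descriptive pilot.

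Several other sections bear on what the number counts.

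- **Section 8** allows replacement of participants who discontinue early or complete fewer than 48 of 56 doses, and says "The participants who are replaced will not be counted in the study".
- **Section 10.3.3** says "The study will only use data that is coherent with protocol".
- **Section 5.4** says that available endpoints will go into the analysis.
- **Section 6.2.2** says "Enrollment will be defined as the date all screening criteria are met and individual agrees to participate" and also "Enrollment and screening will be conducted during the same visit".
- **Section 9.5** reports the number and proportion of patients who develop a resistant organism, with a 95% confidence interval. It names no denominator and no interval method.

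**The concern.** Each figure appears twice, in separate sections, so a single typing slip is unlikely. The document gives two different stopping points for enrolment and two different numbers of patients exposed to the intervention.

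The number also fixes the precision of the primary result, because that result is one proportion with its confidence interval. The plan does not say whether patients who are replaced, deviate, or prove culture-negative belong in that proportion. Two teams could follow the document in good faith and report different denominators.

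A secondary point concerns the objective. The précis sets out to demonstrate that topical antibiotics do not lead to resistance, and section 2.1 states a matching hypothesis. Sections 1.1 and 9.2 only aim to describe. A single-arm proportion with no comparator and no threshold cannot demonstrate absence of resistance with either 20 or 40 patients.

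**Working it through.** **1. Can either figure be derived?** No. The documents give no power, expected rate, margin or target interval width. Neither 20 nor 40 can be reproduced, so the arithmetic cannot show which is intended.

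**2. Could 40 be 20 inflated for losses?** The formula is n / (1 − d), with 20 counted patients and loss fraction d, rounded up.

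| Loss d | Enrolled needed for 20 counted |
|---|---|
| 10% | 20 / 0.9 = 22.2, so 23 |
| 20% | 20 / 0.8 = 25 |
| 30% | 20 / 0.7 = 28.6, so 29 |
| 50% | 20 / 0.5 = 40 |

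Only a loss of 1 − 20/40 = 50% links the figures. Section 8 gives no loss rate, over-enrolment factor or cap.

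**3. Could 40 be two groups of 20?** Section 3 specifies one group, and section 9.1 calls the study single arm in the sentence just before the 40. Section 6.2.1 mentions both groups, and section 9.3 mentions review by group. Neither phrase fits the single-arm design. They may be carried over from a different design, but that is inference.

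**4. Could 40 be enrolled and 20 treated?** The wording partly points this way: sections 9.1 and 9.2 speak of enrolling, while the précis speaks of receiving the intervention. The timing of enrolment is unclear, however.

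- Section 4.1 requires a culture with pathogenic growth, and section 6.2.2 dates enrolment from when all screening criteria are met. On that wording a culture-negative patient is never enrolled.
- Section 6.2.2 also puts screening and enrolment at one visit. Section 5.1 places the pre-intervention assessment at the enrolment visit and has the culture result arrive later. On that wording some enrolled patients may never be treated.
- Section 6.2.1 allows screening tests up to 28 days before enrolment, which leaves the order open.

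No passage says that 40 enrolled are expected to give 20 treated, and the précis presents 20 as the study total.

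**5. What does the difference do to the primary estimate?** Section 9.5 names neither an expected count nor a method, so exact (Clopper-Pearson) two-sided 95% intervals and a range of event rates are assumed. With zero events the upper limit is 1 − 0.025^(1/n):

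- n = 20: 1 − 0.025^(1/20) = 16.84%
- n = 40: 1 − 0.025^(1/40) = 8.81%
- ratio: 16.84 / 8.81 = 1.91

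| Observed rate | n = 20 | n = 40 | Width ratio |
|---|---|---|---|
| 0% | 0 to 16.8% | 0 to 8.8% | 1.9 |
| 10% | 2/20: 1.2 to 31.7% | 4/40: 2.8 to 23.7% | 30.5 / 20.9 = 1.46 |
| 20% | 4/20: 5.7 to 43.7% | 8/40: 9.1 to 35.7% | 38.0 / 26.6 = 1.43 |

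**The case against.** The strongest defence is that the two figures count different things: 40 enrolled at the visit where the swab is taken, and about 20 who grow a pathogen, are treated and complete. Section 5.1 supports a swab at enrolment with the result afterwards, and culture-negative patients would add to any loss under section 8. The 50% figure is then only arithmetic. The documents give no culture-negative or dropout rate against which to judge it. This stands to the extent that the reading is unstated rather than refuted. It does not remove the conflict, because no passage makes the link and the précis gives 20 as the total in the study.

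A second objection is that this is a descriptive pilot with no test or power claim. The proportion and its interval are valid with either number, and the reported interval will show its own precision. That is correct, and the consequence is not bias. Waiving a calculation explains why 40 has no derivation, but it does not explain why two sections say 20.

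A third objection is that the zero-event case shows the largest contrast. That is fair, and the ratio falls to about 1.4 to 1.5 at observed rates of 10% to 20%. The mismatch in objectives is a separate matter that does not depend on the sample size, and the main point does not rest on it.

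**Conclusion.** The concern holds and must be fixed. The current text sets two sample sizes for one single-arm study, 20 patients apart, and at least one pair of sections has to change or be explained. The contradiction rests on the text alone and needs no assumption. The effect on precision, a ratio between about 1.4 and 1.9, assumes exact intervals and observed resistance rates from 0% to 20%, and also that everyone in the stated number enters the denominator. The documents do not show which figure was approved or intended, and this review does not choose between them.

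**What to change.** 1. State the one approved number in the précis and in sections 3, 9.1 and 9.2.
2. Say whether it counts enrolled, treated or evaluable patients, and whether enrolment comes before or after the culture result (sections 4.1, 5.1, 6.2.1 and 6.2.2). If enrolled and treated targets really differ, give both and the expected loss between them.
3. Name the denominator of the primary proportion in section 9.5, consistent with the replacement rule in section 8, the data rule in section 10.3.3 and the available-endpoints sentence in section 5.4. If evaluable depends on adherence, reconcile the two definitions: 48 of 56 doses in sections 5.4 and 8, and 25 of 28 days in section 9.5.
4. Correct the references to more than one group in sections 6.2.1 and 9.3.
5. As a secondary change, align the précis objective with section 1.1, and do not report a zero or low count as showing that resistance is absent.

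**Cost.** These are wording changes if the approved number is the intended one. A substantive amendment is needed if the two differ. Either way, section 11.1 sends protocol modifications to the IRB. Keeping 20 means accepting the wider interval, and keeping 40 means twice the enrolment given in the précis. No extra enrolment is proposed. The stated conclusion becomes more modest.

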9.3 Interim analyses and Stopping Rules

Safety findings that would temporarily suspend enrollment and/or study intervention until a safety review is convened (*either routine or ad hoc*) to determine whether the study should continue per protocol, proceed with caution, be further investigated, be discontinued, or be modified and then proceed are as follows:

-Number of SAEs overall

-Number of occurrences of a particular type of SAE

-Severe AEs/reactions

-Increased frequency of events

Such findings are presented to the Data and Safety Monitoring Board (DSMB) statistician

to review the events by group to determine whether there are statistical as well as clinical concerns. The statistician reports his findings to a closed session of the DSMB (or to the Safety Officer and/or NIA.) The findings are used to determine what steps will be taken.

9.4 Outcomes

9.4.1 Primary Outcome

Post treatment assessment of presence of antibiotic resistant organism as assessed by nasal swab sent for gram stain, culture and sensitivity

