1.1 Primary Objective

The primary objective is to describe the results of antibiotic resistant organisms after the use of topical antibiotics in the treatment of chronic rhinosinusitis.

The secondary objectives are to investigate 1) the effects of topical antibiotics on patient symptoms as measured by the validated Sino-Nasal Outcomes Test (SNOT-22) and physical exam endoscopic findings as documented by Lund-Kennedy endoscopic scoring system. 2) the adherence to study intervention

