Our department has developed in conjunction with the infectious disease department and the Mayo pharmacy, an easy to implement set of topical antibiotics with easy to use capsules and set dosages for use by our patients. This is a pilot study designed with the hypothesis that topical antibiotics do not cause antibiotic resistance. In addition, data will be collected to investigate symptom and physical exam outcomes in patients undergoing topical antibiotic therapy as secondary outcomes. The study will be conducted on existing patients who would otherwise receive treatment with topical antibiotics as standard of care.

Moreover, many of patients who have recalcitrant chronic rhinosinusitis are infected by the bacteria pseudomonas aeruginosa. The use of the fluoroquinolone class of antibiotics is a treatment of choice for this pathogen. In 2008, the US Food and Drug Administration issued a "black box" advising manufacturers to warn providers and patients of risk increased risk of tendinitis, tendon rupture, peripheral neuropathy. A well-studied, viable alternative to oral fluoroquinolone that works well without the associated risks is warranted.

Finally, poor penetration of oral antibiotics to the sinonasal cavity due to the infection being within a space may limit the efficacy of oral antibiotics as a treatment. In contrast use of topical antibiotics in a patient who has previously undergone sinus surgery, provides a potentially more effective delivery of medication to the infected space⁸.

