2.2 Study Rationale

The interventional regimen is as follows.

Patient will undergo pre-intervention nasal swab from the affected sinus that will be sent for gram stain and bacterial culture and sensitivities.

If pathogen identified in the bacterial culture is pseudomonas aeruginosa, topical tobramycin or gentamycin will be assigned as first line agent pending culture profiles and cost factors. If the sensitivities show resistance to both tobramycin and gentamycin, then levofloxacin will be prescribed.

If the pathogen identified in the bacterial culture is other than pseudomonas aeruginosa, mupirocin will be prescribed. If the pathogen shows resistance to mupirocin, then the patient will be prescribed one of the other three antibiotics will be prescribed pending culture profiles and cost factors

The patient will use the topical antibiotic twice a day for 28 days. This will be accomplished by first proceeding with their normal nasal rinse regimen as prescribed by their physician (this may include saline alone, or saline with budesonide). Twice per day, at the end of each regimen, they perform one additional nasal saline rinse using the Neil Med sinus rinse bottle in the manner outlined on the packaging instructions. However, with this last additional nasal saline rinse, they will open their antibiotic capsule and drop the contents into the rinse bottle prior to rinsing.

Known and potential risks are as follows:

Potential risks of nasal saline irrigation is stinging sensation and burning Potential risks of filling the nasal saline irrigation rinse bottle with water that is too hot is mucosal burns

Potential risks of topical antibiotic administration include local pruritis and inflammation Potential risks of selection antibiotic resistant organisms. Potential risk for hearing loss

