9.5 Data Analyses

Statistical Methods

Continuous patient characters will be summarized with means and standard deviations for features that are approximately normally distributed and with medians, interquartile ranges, and ranges otherwise. Categorical features will be summarized with frequency counts and percentages.

Primary endpoint:

Number and proportion of patients who developed antibiotic resistance organism will be summarized. 95% confidence intervals will be provided for the proportion.

Secondary endpoint:

1) SNOT-22 symptom scores and Lund-Kennedy endoscopic exam score will be summarized as mean (standard deviation) and median (range).

2). Definition of adherence to study intervention will be to complete 25 of 28 days of topical antibiotics and attend the pre-intervention / enrollment visit as well as the post-intervention assessment visit. Number and proportion of patients with adherence will be reported.

3) Audiometric data will be summarized as a mean (standard deviation) and median (range)

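### The primary outcome in 9.4.1 counts any resistant organism present after treatment, while 9.5 counts patients who developed one; patients already resistant at baseline stay in the study and separate the two

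*Combined protocol and SAP*

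**What the plan says.** Section 9.4.1 gives the primary outcome as "Post treatment assessment of presence of antibiotic resistant organism as assessed by nasal swab sent for gram stain, culture and sensitivity". Two other places use similar wording. Section 3 states the aim as "to investigate the presence or absence of antibiotic resistant organisms after treatment of chronic rhinosinusitis with topical antibiotics", and 9.1 makes the post-treatment swab alone the measure of success. The objective in 1.1, to "describe the results of antibiotic resistant organisms after the use of topical antibiotics", also looks only at the state after treatment.

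The analysis section uses a different verb: "Number and proportion of patients who developed antibiotic resistance organism will be summarized", with a 95% confidence interval for the proportion. Two statements of purpose agree with it. The précis says "This is a prospective pilot study to evaluate development of antibiotic resistance in patients with chronic rhinosinusitis", and 2.1 says "This is a pilot study designed with the hypothesis that topical antibiotics do not cause antibiotic resistance".

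Baseline resistance is measured, and it directs treatment. Section 2.2 says "If the sensitivities show resistance to both tobramycin and gentamycin, then levofloxacin will be prescribed" and "If the pathogen shows resistance to mupirocin, then the patient will be prescribed one of the other three antibiotics". Such patients go on to another study drug. Neither the inclusion list in 4.1 nor the exclusion list in 4.2 mentions resistance.

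**The concern.** Presence after treatment and development during treatment are the same quantity only if nobody starts with a resistant organism. This plan admits patients who do. A patient whose baseline organism resists mupirocin, who is given another agent and whose second culture grows the same organism, is an event under 9.4.1. On the natural reading of 9.5 that patient is not.

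No section says how the two cultures are compared, resistance to which drug counts, or whether a baseline-resistant patient is an event, a non-event or outside the denominator. The primary result is a single proportion with its interval, and 9.2 says the data are meant for a larger study. If 9.4.1 is followed as written, that proportion includes resistance present before the first dose and does not answer the hypothesis in 2.1. If the choice is left open, it can be made after the cultures have been seen.

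**Working it through.** The plan gives no resistance rate, margin or power figure, so there is nothing of its own to reproduce. The check has two parts.

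**1. The wording side by side**

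| Place | Quantity | Baseline enters? |
|---|---|---|
| 9.4.1, 9.1, 3 | Resistant organism on the post-treatment swab | No |
| 1.1 | Resistant organisms after use | No |
| 9.5 | Patients who developed one | Implied, no rule given |
| Précis, 2.1 | Resistance developing or being caused | Implied |
| 2.2 | Patients resistant to mupirocin, or to both aminoglycosides, are kept | Used for drug choice only |
| 4.1, 4.2 | Eligibility | No resistance criterion |

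Retention is explicit for the two patterns in 2.2. For any other baseline resistance it follows from the absence of an exclusion.

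**2. Size under assumed rates**

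Inputs from the documents: N = 20 (précis, section 3) and N = 40 (9.1, 9.2), both shown because the documents state both; a 95% interval (9.5). Assumed: the baseline resistance rate, the share that persists, and the exact (Clopper-Pearson) method, since 9.5 names none.

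For x events in n patients, the lower limit is the 0.025 quantile of Beta(x, n − x + 1) and the upper limit is the 0.975 quantile of Beta(x + 1, n − x). For x = 0 the limits are 0 and 1 − 0.025^(1/n); for n = 20 the upper limit is 1 − 0.025^(1/20) = 16.8%.

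*Only the assigned drug counts; 5% resistant at baseline and persisting; no new resistance*

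- N = 20: 0.05 × 20 = 1. Section 9.4.1 gives 1/20 = 5% (0.1 to 24.9); new resistance among the rest is 0/19 (0 to 17.6).
- N = 40: 0.05 × 40 = 2. Section 9.4.1 gives 2/40 = 5% (0.6 to 16.9); new resistance is 0/38 (0 to 9.3).

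*Any tested drug counts; no new resistance*

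| N | Resistant at baseline | 9.4.1, all persist | 9.4.1, half persist | New, judged drug by drug | New, baseline-resistant patients left out |
|---|---|---|---|---|---|
| 20 | 10% (2) | 2/20 = 10% (1.2 to 31.7) | 1/20 = 5% (0.1 to 24.9) | 0/20 (0 to 16.8) | 0/18 (0 to 18.5) |
| 20 | 30% (6) | 6/20 = 30% (11.9 to 54.3) | 3/20 = 15% (3.2 to 37.9) | 0/20 (0 to 16.8) | 0/14 (0 to 23.2) |
| 40 | 10% (4) | 4/40 = 10% (2.8 to 23.7) | 2/40 = 5% (0.6 to 16.9) | 0/40 (0 to 8.8) | 0/36 (0 to 9.7) |
| 40 | 30% (12) | 12/40 = 30% (16.6 to 46.5) | 6/40 = 15% (5.7 to 29.8) | 0/40 (0 to 8.8) | 0/28 (0 to 12.3) |

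The drug-by-drug column assumes every patient has at least one drug to which no baseline isolate was resistant.

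*One case with new resistance:* N = 20, 4 resistant at baseline and all persisting, 1 new. Section 9.4.1 gives (4 + 1)/20 = 25% (8.7 to 49.1). New resistance is 1/20 = 5% (0.1 to 24.9), or 1/(20 − 4) = 1/16 = 6.25% (0.2 to 30.2) with baseline-resistant patients left out.

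**The case against.** The best reply is that 9.4.1 only names the measurement and its time point. The section that specifies the reported statistic is 9.5, and its verb means new resistance. The précis and 2.1 agree, and baseline sensitivities are collected under 2.2, 3 and 6.1. This has force: 9.5 does lean towards new resistance, and a reader should not infer that the reported proportion will certainly include pre-existing resistance. It does not settle the matter. Section 9.4.1 is the formal definition, 3 and 9.1 repeat its post-treatment wording, nothing gives 9.5 precedence, and 9.5 has no rule that makes its verb operational.

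A second reply is that the culture-directed choice in 2.2 largely removes baseline resistance to the drug the patient actually receives, apart from cases such as an isolate resistant to every option. That stands, and it is why the gap is small on the assigned-drug reading. The larger gaps need the any-tested-drug reading together with assumed prevalence and persistence. They show what could happen, not what is likely.

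A reader might also infer from 5.2, which describes the post-treatment swab as one of mucopurulence, that patients whose sinus has cleared cannot be assessed. The documents do not support that. Section 3 (for the post-intervention visit) and 6.1 ask only for a swab from the affected sinus. The wording is inconsistent, but it does not show that such patients are lost.

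**Conclusion.** The point holds: the outcome definition and the analysis name different quantities, and retaining baseline-resistant patients makes the difference real. Followed as written, 9.4.1 does not answer the hypothesis in 2.1, so this is more than a missing detail. The difference ranges from one patient in 20 (assigned drug, 5% assumed) to six in 20 (any tested drug, 30% assumed, full persistence). None of these rates comes from the documents.

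A reader might go further and say that the mismatch invalidates a test or a decision rule. It does not: 9.2 describes a descriptive pilot, and there is no hypothesis test or go/no-go criterion for the primary outcome. What is affected is the meaning of the one primary proportion and of the figure carried to the larger study. Persisting baseline resistance still has interest, since 2.2 lists selection of resistant organisms as a risk, but it should be reported as a separate quantity.

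**What to change.** - Align 1.1, section 3, 9.1, 9.4.1 and 9.5 on new resistance: a post-treatment organism resistant to a drug that was tested at baseline and to which no baseline isolate from that patient was resistant.
- Use as denominator the patients at risk for that event: the relevant drug was tested on the baseline isolate and no baseline isolate was resistant to it. If any of the four study antibiotics counts, one such drug is enough, so a patient resistant only to mupirocin stays in if another study drug was tested and none of the isolates resisted it.
- State before analysis whether the assigned antibiotic or any of the four study antibiotics defines the event.
- Report persisting baseline resistance as its own row.
- State that a post-treatment culture with no growth counts as no event, and reconcile the swab wording in 5.2 with section 3 and 6.1.

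Splitting new resistance by same or newly appearing species, and a row for replaced patients who have a post-treatment swab, are optional.

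The cost is mainly rewording, because both cultures with sensitivities are already planned. Isolates must be matched within patient, the site must confirm that both panels test the drugs that count, and patients whose relevant drug was not tested at baseline leave the denominator.
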